**Using fMRI-guided TMS to Increase Central
Executive Function in Older Adults
(MCI_Sub)**

NCT04176406

This document includes the study protocol and the statistical plan approved on March 1st 2020.

Study Protocol:

This experimental supplement is focused on applying TMS to a cortical network node in 30 patients diagnosed with MCI or found to be at risk for cognitive impairment (This cohort will be referred to as "MCI patients", but includes subjects with diagnosed MCI and subjects not currently diagnosed, but at risk for cognitive impairment as defined by criteria below). This blinded, sham-controlled trial will feature a mixed model 2 x 3 x 2 x 2 cross-over design, with rTMS Type (active, sham), Difficulty Level defined by accuracy (easy, medium, hard levels), Stimulation Location (Network, Activity target), and Group (healthy OAs, MCI) as factors. As such, this design reflects the fact that all subjects receive both active and sham rTMS applied to up to two different scalp locations during a WM task at up to three levels of difficulty. Study procedures are listed in **Table 3**. Thirty healthy OAs (age range: 55-80 years) and thirty MCIs (age range: 55-80 years) will participate. In the first session, which will take about 2 hours, participants will be consented and screened for the study, submit a saliva sample for genetic testing, determine TMS motor threshold, and then learn and practice the WM task. The next visit will involve a structural MRI and fMRI recorded from both groups while they perform the WM task. Cortical locations within the FPN (Network target) and DLPFC (Activity target) will be used as targets for rTMS will be chosen from an analysis of subject-specific fMRI activations from the WM task completed in this MRI Session. This session, which will last up to 3 hours, will be followed by up to four sessions of rTMS + MRI, each lasting about 3 hours. These rTMS+MRI sessions will begin ~1 week after the MRI Session, to allow for time to process the imaging data. rTMS+MRI sessions (involving active or sham rTMS and Network or Activity targets) will use coil locations and rTMS device intensities based on realistic head modeling the MRI will collect structural and resting state information.

Working Memory task. In order to test for cognitive performance differences in response to TMS, we will rely on a validated WM task that has shown (1) reliable univariate activity in response to parametric increases in set size or load, 2) multivariate connectivity increases in response to load, and (3) reliable deficits in MCIs using similar stimuli and paradigms. Each trial comprises a set of presented words. On "rehearse" trials, individuals subvocally rehearsed a list of words across a memory delay. On "reorder" trials, individuals mentally rearranged a list of words based on the weight of the objects that the words referred to. Individuals are then probed on the correct order or position of a random word from the array. After scanning, individuals administered a surprise LTM recognition test on words processed in both conditions.

Stimuli in this experiment consisted of 504 words selected from the Medical Research Council Psycholinguistic database (http://www.psych.rl.ac.uk/MRC_Psych_Db.html). The words are 2-13 letters in length and moderate frequency, highly concrete, and highly imageable. These words were used to construct three separate lists of 168 words matched for length, frequency, concreteness, and imageability. Two of the word lists were used for the WM tasks, whereas words from the third list were used as foils for the subsequent LTM recognition test. For the two WM word lists, unique word triplets were constructed in a pseudo-randomized manner. The authors inspected the triplets to ensure that there was no ambiguity in terms of the relative referent weight or pronunciation of the words. The two WM word lists were counterbalanced between subjects and WM condition.

SALIVA SAMPLE: A saliva sample will be obtained from healthy volunteers and MCI patients in this cohort and will be used to perform APOE genetic testing, a risk marker for Alzheimer's Disease. Samples will be obtained by administration of a cheek swab and stored in a secure environment. Subject samples will be deidentified and labeled with the subject study number. Genetic testing will be performed at the Biofluids Shared Resource.

Imaging acquisition and preprocessing. Three forms of structural images will be acquired: **1) full-brain high-resolution T₁-weighted structural images** (inversion recovery prepared 3D SPGR) with full coverage of the head and neck, (TR = 500ms; TE = 20ms; FoV = 24cm²; image matrix = 256x256; voxel size = 0.94 x 0.94 x 1mm), and **2) echo-planar (EPI) sensitivity encoding (SENSE) DWI images** with the same orientation (TR = 2000 ms; FoV = 24 cm²; image matrix = 128²; voxel size 0.94 x 0.94 x 1 mm; b-value = 1000 s/mm²; 1 repetition; 36 diffusion-sensitizing directions). In addition, two forms of functional images will be collected: 1) for **resting state EPI** functional imaging data, which will be used to estimate RSFA, we will acquire 24 slices parallel to the AC-PC plane using a BOLD-sensitive gradient-echo sequence with EPI k-space sampling, at TR of 2s (TE: 35ms; FOV: 25.6cm; voxel size: 63mm), and 2) **event-related EPI**, which uses the same scan parameters and will measure the global reactivity to our Working Memory Task.

TMS methods. Coil targeting will be achieved using frameless stereotaxy (BrainSight: Rogue Research, Montreal). TMS is applied with a figure 8 coil based on 100% resting motor threshold (rMT)⁵⁸, though TMS intensity will also be informed by E-field modeling (described below). TMS will be delivered consecutively over

the individualized target region, based on the cortical site with the highest computed controllability (Network target) or parametric activity (Activity target), using a MagVenture stimulator. Neuronavigation (BrainSight, Rogue Research, Canada) and a robot (SmartMove, ANT, Netherlands) will be used to optimize the targeting. Brain atrophy could also reduce TMS effectiveness because it increases the distance between scalp and the cortex but this potential confound is addressed by adjusting TMS intensity using the E-field computation. In visits 3 to 6, participants will perform the Working Memory Task while active or electrical sham stimulation is delivered using an A/P Cool-B65 coil (MagVenture, Denmark). In a stimulation trial, twenty-five pulses of 5Hz rTMS will be delivered at 100% of the effective E-field. Sham rTMS will be administered with a sham coil equipped with shielding to block magnetic field output but retain the auditory and some of the tactile aspects of active stimulation. This method reproduces the somatosensory sensations as the magnetic field stimulates scalp muscles, and produces the same acoustic artifact than the active stimulation, without inducing current in the cortex⁵⁹.

DWI Structural Connectivity. *Whole-brain tractography.* As in our prior DWI tractography work, Dipy⁶⁰ will be used to generate connectomes representing structural connections between all cortical regions in the Harvard-Oxford Atlas. For structural connection matrices, network edges are defined by the number of tractography streamlines between all nodes of the target network.

Event-related fMRI analyses, functional connectivity and graph theory measures. The Frontoparietal network (FPN) is identified by standard atlas⁶¹, and will be validated with voxelwise independent component analysis (ICA). Task-related connectivity is measured using beta-series correlations²⁰, which estimates a time-series by examining region-by-region interactions that are modulated by task conditions. SMEs for activity and connectivity will be analyzed with a Group (healthy OAs vs. MCIs) x Targeting (Network-based vs. Traditional) x Stimulation (Active vs. Sham) ANOVA using SPM⁶². All matrices are evaluated for descriptive graph-theoretical properties (including degree and controllability) using the Brain Connectivity Toolbox.

E-field Modeling. In order to determine the *intensity* of network-based targeting, we will use electric field (E-field) modeling. The BSEL lab has extensive experience with the creation of anatomically realistic E-field models of transcranial electric and magnetic stimulation in humans, which have been applied to healthy OA populations in ongoing NIH-funded projects by Co-I's [name] and [name] (U01-AG050618), using SimNIBS software⁶³. A detailed model of the TMS coil is combined with a detailed head model. Isotropic tissue conductivities are assigned to the various tissue compartments. Critically, this method will also include anisotropic conductivity in the white matter based on the DWI data. We will carry out E-field simulations over a range of coil orientations and tilts to predict maximal activation of the FPN. The target node (i.e., the node with the highest controllability, identified above) will be used as the center of a 3×3 grid for positioning the coil in simulations of the E-field corresponding to these 9 coil positions and 6 orientations (54 combinations). The simulation E-field maps will be extracted and correlated, voxel-to-voxel, with the fMRI activation and the simulation that yields the highest correlation is selected as the target coil position and orientation.

Statistical Plan:

Power analysis. Our labs have considerable experience with combining neurostimulation and neuroimaging. Through the parent award we have enrolled 85 individuals in multiday memory protocols and results from these data reflect the size of potential future TMS effects. Power calculations were therefore conducted in R software (R Development Core Team, 2016) using the repeated-measures ANOVA module. With N=80 subjects, in a mixed-effects design consisting of 4 repeated measurements per subject (2 groups x 2 TMS targeting [network-based, traditional targeting]), Cohen's $d = 0.9$ for each of the main effects, with interaction effects between 0.7-0.9, attaining an average power of 0.8 at an overall significance level of 5%.

Analytical Rigor. In our analysis phase, we will ensure scientific rigor in the following ways. To address bias in ANOVAs due potential violation of the sphericity assumption in Studies 1 and 2, we will estimate sphericity and correct for this bias using a Greenhouse-Geisser correction. In order to ensure replicability in our findings, we will report analytical procedures according to the Committee on Best Practice in Data Analysis and Sharing (COBIDAS) report for fMRI data analysis. Finally, to ensure generalizability of our findings, we will perform a k-fold cross-validation on all fMRI data analyses. In k-fold cross-validation, the data is divided into k independent subsets. On each fold, one subset is held out as the test set, the others are used for training. Empirical studies suggest that choices of k in the range of 5 to 10, yield good results in practice.

Consideration of sex as a biological variable. We will fulfill this recent NIH mandate by including both sexes in the research and by including gender as a covariate of interest in all analyses. Because this is an exploratory study, we have no a priori predictions on how gender might influence the TMS-imaging results. Although we may be underpowered to observe sex differences, the outcome of this Administrative Supplement can be used to estimate effect sizes to adequately power gender differences in future larger-scale studies.

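### Cheap improvement: add a session-number term to the cross-over analyses, and confirm that active and sham are balanced over the rTMS visits

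*Combined protocol and SAP*

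**What the plan says.** The opening of the Study Protocol describes a sham-controlled cross-over "with rTMS Type (active, sham), Difficulty Level defined by accuracy (easy, medium, hard levels), Stimulation Location (Network, Activity target), and Group" (healthy older adults or MCI). It says that "all subjects receive both active and sham rTMS applied to up to two different scalp locations during a WM task".

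The same WM task recurs throughout. At the first session participants are screened "and then learn and practice the WM task". Then: "The next visit will involve a structural MRI and fMRI recorded from both groups while they perform the WM task". That visit "will be followed by up to four sessions of rTMS + MRI, each lasting about 3 hours". TMS methods confirms that the task is done at visits 3 to 6 under active or sham stimulation.

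The only model written out is under Event-related fMRI analyses: SMEs (not expanded) for activity and connectivity "will be analyzed with a Group (healthy OAs vs. MCIs) x Targeting (Network-based vs. Traditional) x Stimulation (Active vs. Sham) ANOVA". No model for WM performance is written out.

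Counterbalancing is described only for the stimuli, under Working Memory task: "Two of the word lists were used for the WM tasks" and "The two WM word lists were counterbalanced between subjects and WM condition". Analytical Rigor adds a Greenhouse-Geisser correction, and the paragraph on sex adds gender as a covariate. Study procedures are referred to Table 3, which is not in the supplied text. The order and spacing of sessions are not given elsewhere.

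**The concern.** Each participant's active and sham sessions fall at different points on a learning curve. Session number is in neither the factor list nor the written ANOVA, and nothing else stated stands in for it. Greenhouse-Geisser adjusts for the covariance pattern, not for shifts in session means. Gender does not vary within a participant. The word-list balancing is over subjects and WM condition, not over sessions.

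This needs no stimulation effect to persist between visits; practice, fatigue or scanner drift is enough. With a balanced order, the shift inflates the error of the active-sham comparison. With a fixed or unbalanced order, it would enter the comparison itself. Because participants have up to four sessions, incomplete sequences can also unbalance an order that was balanced on paper.

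**Working it through.** **Inputs from the documents.** 30 + 30 participants; up to four rTMS sessions; two stimulation types by two locations.

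**Assumptions.** One condition per visit. Session effects are additive. Let g be the change per session in SDs (σ) of the session-level residual, taken as 0 to 0.3; the documents give no value. The plan states no figure on this point. Its power statement has no session component and gives no within-participant correlation, so it is not used here.

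**1. Baseline variance.** With two active (A) and two sham (S) sessions, a participant's contrast has variance σ²(1/2 + 1/2) = σ². Over 60 participants this is σ²/60 = 0.016667σ².

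**2. Shift in one participant's contrast** = mean session gain under active minus mean under sham.

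| Order | Linear (0, 1, 2, 3)g | Levelling off (0, 1, 1.5, 1.75)g |
|---|---|---|
| AASS | −2g | −1.125g |
| ASAS | −1g | −0.625g |
| ASSA | 0 | −0.375g |

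The mirror orders (SSAA, SASA, SAAS) reverse the sign.

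**3. Balanced order, no session term.** The shifts average to about zero (at most 2g/30 = 0.067g with 30 per group split 8/8/7/7), but their mean square is added to σ². For AASS/ASSA/SSAA/SAAS in equal shares:

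- Linear: (4 + 0 + 4 + 0)g²/4 = 2g². Variance is multiplied by 1.02, 1.08 and 1.18 at g = 0.1, 0.2 and 0.3, equivalent to 60/1.02 = 58.8, 60/1.08 = 55.6 and 60/1.18 = 50.8 participants.
- Levelling off: (1.125² + 0.375²)g²/2 = 0.703g². Multipliers are 1.007, 1.028 and 1.063.
- g = 0: no inflation.

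The size depends on the order set. If ASSA, SAAS, ASAS and SASA are used equally, the linear figure is (0 + 0 + 1 + 1)g²/4 = 0.5g², that is 0.5, 2 and 4.5%.

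**4. With a session term.** Least squares with participant, Stimulation, Location, their interaction, their interactions with Group, and three session terms (240 observations) gives variance 0.016704σ² and drift bias 0. The cost is 0.016704/0.016667 − 1 = 0.2%. It arises only because 30 does not divide by four. The four-order set at the end of step 3, split 8/8/7/7, gives the same 0.016704.

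**5. Power.** This was simulated with 60 participants, within-participant correlation 0.6, a period-balanced square, a true effect of 0.25 SD and 1,000 runs. Adding the term moves power from 84.6 to 85.4% at a drift of 0.1 total SD per session, and from 82.2 to 86.4% at 0.2. In residual units 0.2 is 0.2/√0.4 = 0.32, just above the assumed range.

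**6. One fixed order for everyone.** Adding session terms gives a design matrix of rank 66 for 69 columns: active-sham is not estimable.

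**7. Stopping after two sessions.** Assume 32 per group, with 8 per group stopping. A four-session participant contributes information 1/σ²; a two-session participant with one active and one sham contributes 1/(2σ²); one with two of the same type contributes none.

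- All orders open with one of each: 48 + 16/2 = 56, variance σ²/56 = 0.01786σ².
- Half open with two of the same type: 48 + 8/2 = 52, variance 0.01923σ², which is 7.7% more.
- With 16 per group stopping: 48 against 40, which is 20% more.

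**The case against.** The strongest case against has four parts.

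- **No bias is shown.** A reader might infer that practice biases active-sham by up to 2g, which is 0.2 to 0.6 SD, or 22 to 67% of the planned d = 0.9. That requires every participant to follow AASS or SSAA, linear drift after two earlier exposures to the task, an unsourced g of 0.1 to 0.3, and a d on the residual scale. The text is silent on order and Table 3 may set it. If order is randomised, the expected bias is zero and only precision is at stake. This objection stands in full.
- **The written ANOVA is an imaging model.** If SME means a subsequent-memory contrast, as the long-term memory test suggests, it is a difference within a session and an additive shift cancels. This stands, and limits where the term matters. A factor list also does not prove that the fitted model omits period; it shows only that no such term is stated.
- **One condition per visit is an inference.** Two types by two locations fits four sessions, but stimulation is also described per trial. If active and sham shared a visit, session drift would cancel. The reading is plausible, but it is an assumption.
- **Difficulty is defined by accuracy.** If levels were reset at each visit, some practice gain would be absorbed. The text does not say when they are set.

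None of this removes the case for a term that costs almost nothing and also adjusts for incomplete sequences.

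**Conclusion.** The point holds as a cheap improvement to an exploratory study, not as a defect that invalidates it. No session term is stated, and adding one moves any additive drift out of the error. Under balanced order the gain is 2 to 18% of variance with linear drift in a set that includes AASS and SSAA, 0.7 to 6% if practice levels off, less in sets that mix types early, and nothing if there is no drift. This rests on one condition per visit, additive session effects and an assumed g.

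The documents do not support saying that the active-sham comparison is biased. That follows only under a fixed or unbalanced order, which is a question for the sponsor. Carry-over of stimulation between visits is likewise not shown, and no part of this conclusion depends on it.

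**What to change.** 1. Add session number (categorical, within participant) to the WM-performance analysis, and to the activity and connectivity ANOVA wherever the outcome is not a within-session contrast. A session x group term is optional, since practice may differ in MCI.
2. Confirm that Table 3 or the randomisation list balances condition over session within each group. If it does, only step 1 is needed.
3. If it does not, randomise within group to a period-balanced set in which the first two sessions include one active and one sham (patterns ASSA, SAAS, ASAS, SASA, with locations arranged so that each condition occurs equally often at each session). Participants with fewer than four sessions then still contribute to active-sham.

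Cost: three model degrees of freedom (six with session x group), about 0.2% of variance with complete data and, if step 3 is needed, a randomisation list. No participants, visits or procedures are added. Step 2 cannot be skipped, because the session term does not repair a single fixed order.

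### The design allows one-location participants, but the stated ANOVA in its standard form cannot use their active-sham pairs; a mixed model would keep them

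*Combined protocol and SAP*

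**What the plan says.** The opening paragraph of the Study Protocol says the trial "will feature a mixed model 2 x 3 x 2 x 2 cross-over design", the factors being rTMS type, difficulty, location and group. It then qualifies this: all participants receive "both active and sham rTMS applied to up to two different scalp locations during a WM task at up to three levels of difficulty", and the imaging visit "will be followed by up to four sessions of rTMS + MRI, each lasting about 3 hours". So active and sham are promised to everyone, but a second location and a full set of four sessions are not.

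Two other places read as complete data. TMS methods states "In visits 3 to 6, participants will perform the Working Memory Task while active or electrical sham stimulation is delivered", which is four visits. The Power analysis assumes four measurements on each participant.

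The named inferential analysis is in the section on event-related fMRI analyses: Group "x Targeting (Network-based vs. Traditional) x Stimulation (Active vs. Sham) ANOVA using SPM", applied to activity and connectivity. Power was computed "using the repeated-measures ANOVA module". Under Analytical Rigor, "we will estimate sphericity and correct for this bias using a Greenhouse-Geisser correction". No section defines an analysis set, says who may have fewer locations or sessions, or gives a rule for a participant with missing conditions. No model is stated for working-memory performance.

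**The concern.** Design and analysis do not fit together. A classical repeated-measures ANOVA works on a full within-person table, here two targets by two stimulation types. A participant with one location fills half of it. That half is a complete active-sham comparison, the comparison the trial exists to make. Yet the standard procedure has no place for it and would leave the participant out of every test, including Stimulation and Group x Stimulation, where the data are informative.

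Precision is at stake in a trial of 60. So is a choice left open: with no rule written down, the handling of incomplete participants would be settled after the data are seen.

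**Working it through.** **The plan's own figure.** The Power analysis reports average power 0.8 with 80 participants, d = 0.9 for main effects and 0.7 to 0.9 for interactions, at 5%. Two-sided, 40 per group gives 0.98 at d = 0.9 and 0.87 to 0.88 at d = 0.7. Four independent cells of 20 give 0.81 (normal) or 0.79 (t) at d = 0.9, but 0.60 or 0.58 at d = 0.7, and that ignores the repeated measures. Without the within-person correlation and the tested contrast, the figure can be neither confirmed nor refuted. This point does not depend on it.

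**Inputs from the documents.** 30 + 30 = 60 participants; at most two locations; at most four sessions; active and sham for all. The share of incomplete participants is not given, so every rate below is an assumption.

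**How many would be complete.** Assume one target-by-type condition per session, and each session missed independently with probability p. Complete participants = 60 x (1 - p)^4:
- p = 5%: 60 x 0.815 = 48.9, about 49
- p = 10%: 60 x 0.656 = 39.4, about 39
- p = 15%: 60 x 0.522 = 31.3, about 31

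**What the discarded pairs are worth.** Let s2 be the residual variance of one cell and tau2 the between-person variance of the stimulation effect. The variance of one person's active-sham estimate is
- two locations: tau2 + s2
- one location: tau2 + 2 x s2

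Suppose 30% have one location: 42 complete and 18 one-location participants, the 18 split evenly between locations. Information is the sum of the reciprocals.

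| | 42 complete only | All 60 | Ratio | SE ratio |
|---|---|---|---|---|
| tau2 = 0, s2 = 1 | 42 | 42 + 18/2 = 51 | 51/42 = 1.21 | 1.10 |
| tau2 = s2 = 1 | 42/2 = 21 | 21 + 18/3 = 27 | 27/21 = 1.29 | 1.13 |

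If all 18 share the same location and the stimulation effect may differ by location, generalized least squares gives a gain of 18% to 25%, so the complete-case SE is 8% to 12% larger.

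**In terms of power.** The ratios make the 60 participants worth 42 x 51/42 = 51 or 42 x 27/21 = 54 complete ones. Take Group x Stimulation as a two-group t comparison of per-person contrasts, with d on the scale of complete participants and equal losses in the two groups:

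| Complete-equivalent total | Power, d = 0.7 | Power, d = 0.9 |
|---|---|---|
| 60 (no loss) | 0.76 | 0.93 |
| 54 | 0.71 | 0.90 |
| 48 | 0.66 | 0.86 |
| 42 (complete cases) | 0.60 | 0.81 |

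Keeping the 18 lifts power from the 42 row to the 54 row when tau2 = s2, or to between the 48 and 54 rows when tau2 = 0.

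**Simulation check.** An active-sham effect of 0.35 was simulated with between- and within-person SD 0.7 each, no variation in the effect between people, one-location participants arising at random, and 300 runs per scenario. Complete-case against mixed-model power was 0.80 against 0.92 with 40% one-location, and 0.73 against 0.91 with 50%. For the 40% case the closed form gives 36 complete participants (0.83) against 36 + 24/2 = 48 equivalents (0.92), which agrees within Monte Carlo error of 1 to 3 points. At 20% the simulation gave 0.92 against 0.98. The closed form gives 0.92 against 0.95, and the smaller gain is the safer one to quote.

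**Difficulty.** Difficulty is a design factor but not a factor in the stated ANOVA. A participant without one difficulty level still fills all four Targeting x Stimulation cells and is not lost from it.

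**The case against.** The strongest reply is that nothing in the plan says incomplete participants are dropped. That is right. Exclusion follows from the usual form of the analysis, and some SPM factorial models accept unbalanced cells, in which case a one-location pair would still inform Stimulation. But the plan does not say that it relies on such a model.

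A reader might take the Greenhouse-Geisser sentence as proof that every cell is needed. It is not. Targeting and Stimulation have two levels each, so every within-person effect has one degree of freedom and the correction does nothing. The sentence also refers to Studies 1 and 2, which this document does not define.

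A reader might infer that incompleteness is certain. The wording may only state a maximum, and TMS methods and the Power analysis both read as four sessions for all. If so, nothing is lost, and the plan should say so.

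A reader might also infer that the retained group with cognitive impairment would be a fitter subset and its comparisons biased. More missed sessions in one group do not by themselves bias a comparison. Bias in Group needs missingness related to outcome within a group. Bias in Group x Stimulation needs the stimulation effect to vary with whatever drives the missingness. The documents give no reasons for fewer locations or sessions, so they neither show nor exclude this.

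The terms mixed model and mixed-effects do appear, but they describe the design. No random effects or likelihood estimation are specified.

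Two limits also stand. A one-location participant has no within-person Targeting contrast, so the comparison of targets gains little. And the plan calls the study exploratory, which lowers the stakes.

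**Conclusion.** The point holds as a gap between a design that permits one-location participants and an analysis that, in its standard form, cannot use them. The supported consequence is lost precision on Stimulation and Group x Stimulation: a complete-case standard error about 10% to 13% larger if 30% have one location split evenly, or 8% to 12% larger if they all share one. These figures rest on the assumed 30%, on tau2 between 0 and 1 times s2, and on the ANOVA being run on complete cases. If everyone completes four sessions, the loss is zero. Automatic deletion, selection bias and exclusion through a missing difficulty level are not supported by the documents. This is a cheap improvement, not a flaw that invalidates the trial.

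**What to change.** State whether two locations and four sessions are planned for every participant and, if not, the reasons for fewer. Then:

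- **Regional and graph outcomes, and working-memory performance:** make a REML linear mixed model the primary analysis. Fixed effects: Group x Targeting x Stimulation, session order (period), and Difficulty where used. Random effects: participant intercept and, where estimable, Stimulation and Targeting slopes. Use Kenward-Roger degrees of freedom. The session-order term matters because, if later sessions are the ones missed, practice effects could otherwise be mixed with condition.
- **Analysis set:** every participant with at least one stimulation session.
- **Sensitivity analysis:** the ANOVA on participants with all four cells.
- **Voxelwise SPM analysis:** a subject-blocked factorial model that keeps unbalanced cells, stated as such.

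The mixed model relies on data missing at random, so reasons for missed sessions should be reported by group. The cost is plan wording, standard software and a separate specification for the voxelwise model. The random-effects structure may need simplifying if the model does not converge, and the order of simplification should be fixed in advance.

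### The power statement describes a different design from the one planned (80 versus 60 participants, mislabelled repeats, no active/sham factor), and no working-memory score or main contrast is named for it to refer to

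*Combined protocol and SAP*

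**What the plan says.** **Purpose.** The title is "Using fMRI-guided TMS to Increase Central" Executive Function in older adults. The Working Memory task section introduces the task "In order to test for cognitive performance differences in response to TMS".

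**Design.** The opening paragraph of the Study Protocol sets out a 2 x 3 x 2 x 2 crossover with rTMS Type, Difficulty, Location and Group as factors. It says that "all subjects receive both active and sham rTMS applied to up to two different scalp locations during a WM task". On size: "Thirty healthy OAs (age range: 55-80 years) and thirty MCIs (age range: 55-80 years) will participate". Up to four rTMS sessions are planned. TMS methods confirms the setting: "In visits 3 to 6, participants will perform the Working Memory Task while active or electrical sham stimulation is delivered".

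**Task.** There are two trial types. On rehearse trials the words are repeated silently; on reorder trials "individuals mentally rearranged a list of words based on the weight of the objects that the words referred to". Then: "Individuals are then probed on the correct order or position of a random word from the array". Accuracy appears in the design only as the basis of a factor: "Difficulty Level defined by accuracy (easy, medium, hard levels".

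**Analysis.** The event-related fMRI section gives a Group x Targeting x Stimulation ANOVA for imaging measures of activity and connectivity. Analytical Rigor adds a Greenhouse-Geisser correction for ANOVAs, with no outcome named.

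**Power.** The Power analysis paragraph takes N=80 and four repeated measurements per person, glossed as two groups by two targeting methods. It takes d=0.9 for main effects and 0.7 to 0.9 for interactions, and reports power averaging 0.8 with overall significance set to 5%.

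**The concern.** A power statement should tell the reader what the planned trial can detect on the measure it cares about. This one has a different sample size, a factor layout that cannot be right as labelled, and no outcome. As labelled, it also omits the factor that makes the trial sham-controlled.

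The related gap is on the behavioural side. rTMS Type is a factor during the working-memory task, but the plan does not say which score is analysed, whether it uses rehearse, reorder or pooled trials, or which effect is the main one. Trial type is not among the design factors, so all three choices remain open. Accuracy is the obvious score, but it also defines Difficulty. If levels were reset to accuracy during stimulation, accuracy would be held roughly constant and could not show a TMS effect. No section says when levels are set.

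At stake is whether a reader can judge the size of the trial, and whether score, trial type and contrast could be settled after the data are seen.

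**Working it through.** **1. Inputs.** From the Study Protocol: 30 + 30 = 60 participants; rTMS Type 2, Difficulty 3, Location 2 (all within-subject); Group 2 (between-subject). From Power analysis: N=80, four repeats, d=0.9 (main effects), d=0.7 to 0.9 (interactions), 5%, average power 0.8. Not stated: outcome, SD, within-subject correlation (rho), the scale of d, sidedness. I assume two-sided tests and vary rho.

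**2. Layout.** The design has 2 x 3 x 2 = 12 within-subject cells. Two groups by two targeting methods leaves only targeting within subject, so 2 repeats, not 4. rTMS Type x Location would give 2 x 2 = 4, matching the maximum number of sessions. The text may be a mislabelling of that, but it does not say so.

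**3. Trying to reproduce 0.8 at N=80 (40 v 40).** Take one measure per target and d in raw SD units.
- Group main effect: SD of a person's mean = sqrt((1+rho)/2). At d=0.9, power is 0.985 or more for rho from 0 to 0.9.
- Targeting main effect: SD of the difference = sqrt(2(1-rho)). At rho=0 the noncentrality is 0.9/1.414 x sqrt(80) = 5.69, so power is about 1.00.
- Group x Targeting: noncentrality = d/sqrt(2(1-rho)) x sqrt(40/2). At rho=0 and d=0.7, 0.8, 0.9, power is 0.59, 0.71, 0.80 (average 0.70). At rho=0.3 the average is 0.84.
- Average over the two main effects and the interaction at rho=0: (1.00 + 1.00 + 0.70)/3 = 0.90, not 0.80.

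A value near 0.8 arises in two ways. One is the interactions alone, with an unstated rho between 0 and 0.3. The other is 80 people split into four independent cells of 20 compared pairwise at d=0.9 (0.79 by t test), which is not a repeated-measures design. The figure is therefore not reproduced, but it is not shown to be impossible either.

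**4. The same interaction at 30 v 30.** Average power is 0.58 at rho=0, 0.72 at rho=0.3 and 0.85 at rho=0.5. On this scale, whether 0.8 survives at 60 depends on a correlation the plan does not give.

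**5. Power with d on the contrast's own SD scale** (noncentral t, noncentrality d x sqrt(n/2), n per group):

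| | d=0.9 | d=0.7 |
|---|---|---|
| 40 v 40 | 0.98 | 0.87 |
| 30 v 30 | 0.93 | 0.76 |

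**6. Detectable differences for the planned trial** (80% power, complete data). The paired effect is the mean active-sham difference divided by the SD of the within-person differences, with noncentrality d x sqrt(n):

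| Contrast | n | Detectable |
|---|---|---|
| Active minus sham, all | 60 | 0.37 |
| Same, at the power paragraph's N | 80 | 0.32 |
| Active minus sham, one group | 30 | 0.53 |
| Group difference in the effect | 30 v 30 | 0.74 |

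The scale matters. With one measure per condition, the SD of a difference is sqrt(2) times the residual within-person SD, so 0.368 becomes 0.368 x 1.414 = 0.52 in residual SD units.

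**The case against.** **The active-versus-sham test is already there.** rTMS Type is a two-level design factor during the working-memory task, and its main effect is the active-sham contrast. The sphericity correction points the same way: two-level factors do not need one, and Difficulty is the only three-level factor, so an ANOVA on the full layout seems intended. Most of this stands. A reader might infer that the plan contains no test of active against sham, and the documents do not support that. The sphericity argument is only an inference, because that paragraph refers to Studies 1 and 2 and names no outcome. What is missing is narrower: the score, the trial type and the designated main contrast.

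**Working memory may not be the main question.** No primary outcome is declared, the power paragraph concerns Group and targeting, and the sex-differences paragraph calls the study exploratory. This also stands in part. Network versus Activity targeting is an equally plausible focus, so the review should not choose the contrast for the team. But being exploratory does not supply an outcome, and it does not reconcile 80 with 60.

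**60 may be enough.** This is fair. At d=0.9 on the contrast's own scale, 30 v 30 gives 0.93.

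**Conclusion.** The Power analysis paragraph does not describe the planned trial. The sample size (80 against 60) and the count of repeats (four stated, two implied) are contradictions in the text and need no assumption. The 0.8 cannot be checked, and is not shown to hold at 60, because the outcome, SD, correlation and effect-size scale are absent.

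In size, moving from 80 to 60 raises the detectable active-sham difference from 0.32 to 0.37 SD of the within-person differences, and lowers two-group power at d=0.7 from 0.87 to 0.76. These figures assume two-sided 5% tests and complete data.

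Two stronger readings should be resisted. A reader might infer that the trial is underpowered or that 0.8 is an arithmetic error; the missing inputs allow neither conclusion. A reader might also infer that many rTMS effects will be tested uncorrected; the plan does not say so, and it mentions an overall 5% level.

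The working-memory gap is real but partly one of missing detail in a study that describes itself as exploratory. Both parts are worth correcting, and neither invalidates the design.

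**What to change.** **Power analysis.** Restate the power at N=60 for a named outcome and contrast. Describe the within-subject factors correctly (for example rTMS Type x Location, if that was meant), and give the assumed correlation and the scale of the effect size.

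**Statistical Plan, before unblinding.**
- The team names one working-memory score from visits 3 to 6, and says whether it uses rehearse, reorder or pooled trials.
- The team names one main contrast involving rTMS Type: overall active minus sham, or its interaction with Location, as it intends. Other rTMS effects become secondary.
- Analyse the score in a mixed model with the design factors, gender as a covariate (already promised) and participant random effects, so that people with fewer than four sessions or only one location still contribute.
- If accuracy is the score, state that difficulty levels are fixed before stimulation. If a level-based score is used instead, drop Difficulty as a factor in that model, since it cannot be both outcome and predictor.

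**Cost.** A rewritten power paragraph and one added model. No new data are needed, because the task is already performed under stimulation. The restated power may look less favourable, and effects not chosen as the main contrast lose confirmatory standing.
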